7.2.7 Discomfort or increased pain on insertion, during use or with withdrawal

Like procedures involving percutaneously inserted needles (e.g., injections, needle electromyography, acupuncture), discomfort associated with test stimulation/placement of the stimulator lead is possible. Usually the discomfort is transient and improves shortly after needle insertion. Subjects are asked to provide feedback on pain or discomfort experienced during the procedure. Symptomatic relief with local anesthesia may be used to reduce discomfort.

Electrical stimulation is perceived by the subject as tingling or vibratory sensations. These sensations are expected to be comfortable, however it is possible that they can cause discomfort or pain. Uncomfortable sensations are likely directly related to stimulus intensity, which is adjusted on the PNS stimulator. Pain is typically associated with higher intensity levels. During the lead placement procedure, stimulus intensity is adjusted to the determine the minimum and maximum range of intensities that produce comfortable

sensations without discomfort or pain. Prior to completion of the lead placement procedure, an appropriate stimulation intensity is set. Further, the subject can select from a range of intensities determined by the investigators as safe and unlikely to cause discomfort. If a subject ever feels pain related to stimulation, they can turn down the intensity or turn the stimulator off.

Subjects may experience worsening of pain symptoms or may not obtain any therapeutic benefit from the system. Worsening pain could be caused by natural changes in pain during post-operative recovery and rehabilitation, or may be caused by electrical stimulation, or the presence of the lead. This is a common risk, but worsening pain is expected to be transient, resolving without additional treatment. Subjects can have their stimulation parameters adjusted throughout the study for optimal comfort, or treatment may be discontinued. These risks are mitigated by clinical training on the safe limits of stimulation and the proper placement of the leads.

7.3 Risk-Benefit Analysis

All efforts will be made to reduce the incidence of the potential risks described above. Despite taking all necessary precautions, these events, as well as unanticipated events may still occur. All procedures will be performed by trained attending physicians working within their scope of practice. Practices will be maintained to mitigate the potential risks discussed above. If an event occurs, the potential for significant harm is low because the risks presented have non-serious consequences. Further, the subjects in the Treatment Group may gain no direct benefit from electrical stimulation. This investigation has inherent risks to Treatment Group subjects which are justifiable based on the following rationale:

The insertion of needles targeting the femoral or sciatic nerves carries the risk of damaging unintending structures including nerves, blood vessels, organs, and joint spaces. The risk of damage to these structures is reduced by utilization of ultrasound guidance, knowledge of anatomic landmarks, and awareness of needle position and depth. The physicians performing placement of the PNS system are trained in regional anesthesiology with experience in the placement of peripheral nerve block catheters or will receive the appropriate training necessary to safely conduct the procedure. Lead placement for the peripheral nerve stimulator requires a needle distance that is further from the target nerve than does placement of a peripheral nerve block catheter (5 – 30 mm and 2 mm, respectively). The increased distance between target nerve and needle should lower the risk of injury to unintended structures. Further, evoked responses to electrical stimulation are used to guide lead placement (i.e. the needle is advanced slightly; once stopped, stimulation is applied and the subject is evaluated for responses; process is repeated as needed). If damage to a nerve occurs from direct mechanical injury or nerve compression secondary to hematoma, symptoms are expected to occur within 24-48 hours. Subjects are instructed to contact study personnel if any changes in medical status occurs.

The risk of irritation or infection from needle insertion is reduced by cleaning the lead insertion site using aseptic technique, sterile test needles, and lead introducer needles. Needles are not reused. Subjects with systemic infection and/or immunosuppressive disorders will be excluded. Subjects are instructed to contact study personnel in case of any change in medical status.

The risk of discomfort associated with needle insertion or electrical stimulation are possible. Discomfort arising from needle insertion is usually transient and resolves shortly after needle insertion. Subjects are asked to provide feedback regarding sensations, pain, or discomfort experienced during the lead placement procedure and throughout the study. The test needle and lead introducer needle can be repositioned as necessary to obtain the most comfort. Local anesthetic will be used as needed to reduce discomfort during the procedure. Stimulation parameters can be adjusted throughout the study to obtain the most comfort.

Lead fracture and subsequent retention of lead fragments is possible. Study personnel will inspect the lead upon removal to look for signs of fracture. Usually, no treatment is required for retained fragments unless an infection or granuloma occurs. The study investigators will determine the most appropriate course of treatment.

The potential benefits expected from successful treatment include reduction in pain intensity after TFA or TTA surgery in the acute post-operative setting, decrease in the incidence and/or severity of chronic post-amputation PLP or RLP, reduction in opioid medication use, increased tolerance for rehabilitation and faster functional recovery. This research may benefit future patients with post-operative pain following TFA or TTA. Additionally, the PNS system used in this study has not been formally investigated to be used in the acute post-operative setting after TFA or TTA. Information regarding its efficacy and utility in this setting may be useful in determining the most appropriate applications for this system in the future. The potential risks associated with the use of this PNS system have non-serious consequences and are expected to be uncomplicated to manage. The risks are justifiable by the potential benefits. The information to be gained in this study may be used to refine further research within the area of peripheral nerve stimulation for the management of post-operative pain.

8.0 Data and Safety Monitoring

Primary and secondary outcomes will be recorded at each follow-up visit. Study investigators will retain study-related documents in double-locked filed cabinet in 2C-117. The PI or an investigator will conduct a data and safety monitoring review once every 8 weeks in which Case Report Forms and any AE forms are evaluated. Safety information is also assessed at outpatient study visits and by telephone calls. If study investigators determine that the PNS treatment is unsafe to continue (i.e. systemic infection, increased pain that is intolerable to the subject, need for implantable electronic device that requires discontinuation of the PNS), then PNS will be discontinued as appropriate.

8.1 Serious Adverse Events

Serious Adverse Events (SAE) will be recorded on Form AE and the IRB will be notified within 5 days of occurrence. Monitoring for SAEs will occur at each follow-up encounter. Subjects will be asked if they are experiencing any increased discomfort, pain, skin irritation, or bleeding. At the outpatient follow-up visits, the PNS lead exit site will be examined and the stimulator device will be interrogated to ensure proper functioning. Any adverse event will be investigated and managed as appropriate. Subjects are instructed to notify study personnel by [contact]) in case of any changes in medical status as soon as possible. If investigators need to be reached after normal business hours, subjects will be given instructions on how to page study staff who call the subject as soon as possible.

Details regarding any observed adverse event and its relation to the PNS system will be collected on Form AE. The severity of the AE will be classified as mild (event that causes mild discomfort or inconvenience and resolves without treatment), moderate (event that requires medical intervention or medication to treat), or severe (event that requires intervention to prevent permanent impairment or damage, an event that requires or prolongs hospitalization, or an event that is disabling, causing permanent damage, life threatening, or causing death). Any treatment necessary related to the AE will be documented. AEs will be followed to resolution, even if a subject is discharged from the study early. Adverse events will be documented and reported so that the safety profile of this system may be further understood.

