5.4.2 Exclusion Criteria

- 231 Exclusion criteria are systemic infection, immunosuppressive disorder, implanted electronic devices,
- pregnancy, previous allergy to skin contact materials and/or anesthetic agent altered mental status, inability
- 233 to provide consent, greater than 180 morphine equivalents (MED) per day.

234 5.5 Study Plan

- The study includes 13 Visits. Please refer to the Appendix for a schedule of study procedures for both
- 236 groups as well as outcomes measured at each visit.
- Patients planned for nontraumatic TFA or TTA will be screened by the study investigators who are working
- on the Acute Pain Service (APS). APS is usually consulted for all transferoral and transtibial amputations
- 239 to provide perioperative anesthesia, which typically includes placement of a peripheral nerve catheter for
- local anesthetic blockade. When a potential subject is identified, study investigators will begin a chart
- review for screening purposes. The investigators will review the medical record of potential subjects and
- complete Form 00 (Screening and Demographic Information). Chart review will include the collection of
- name, social security number and date of birth from CPRS, the ORC, and the Vascular Clinic. Protected
- Health Information (PHI) will be used to locate and review appropriate medical records (CPRS and paper
- medical records) to determine study eligibility. If a subject appears to meet all eligibility criteria (see
- 245 incident records) to determine study engionity. If a subject appears to ineet an engionity enterta (see
- Section 5.4. Eligibility), then he/she will be contacted by study investigators and given recruitment
- 247 materials detailing study objectives, randomization, procedures, follow-up encounters, assessments, and
- 248 potential risks and benefits. The subject will be provided with patient information pertaining to the
- 249 peripheral nerve stimulator system under investigation. If permitted by the subject, a sponsor representative
- or their designee may be present at any of the study visits to advise on material handling and answer
- questions as needed.

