5.5.3 Visit 2B: Daily hospital evaluations until discharge

Subjects in both groups will be evaluated by study investigators daily until they are discharged. The length of stay is approximately 14 days for TFA per VASQIP 2016 quarter 4 data (Veterans Affairs Surgical Quality Improvement Program). Based on this data, subjects in Group 1 will likely be discharged 7 to 14 days after starting peripheral nerve stimulation. Group 1 subjects will be asked questions to re-assess the stimulation-evoked paresthesia coverage of the leg. Stimulator devices will be inspected to ensure appropriate function. Lead exit sites are inspected for skin irritation, infection, and inflammation. These risks will be minimized by using sterile leads and sterile technique. Maintenance, care of the leads and lead exit sites, and bandage changes will be performed as needed. Subjects in both groups will be evaluated for the presence of phantom sensations, as well as least, worst, and average PLP or RLP according to the Schedule of Study Procedures.

364 .

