5.5.4 Visits 3, 4 and 5: Weekly telephone follow-up evaluations

Visits 3, 4 and 5 consist of weekly telephone evaluations at 1, 2 and 3 weeks after starting peripheral nerve stimulation (Group 1) or discontinuation of peripheral nerve block (Group 2). If issues related to the peripheral nerve stimulator device or leads occur and cannot be resolved by telephone, subjects may be evaluated in the Interventional Pain Clinic as needed.

Subjects are asked to rate their worst, least, and average PLP and RLP (BPI #3, #4, and #5). A medical reconciliation will be completed during each phone evaluation by asking the subject how many pills of narcotic pain medications they have left and querying the Virginia Prescription Monitoring Program Database.

5.5.5 Visit 6: First outpatient clinic evaluation / 30 days after start of PNS

All subjects are asked to return to the Interventional Pain Clinic at 4 weeks after the start of peripheral nerve stimulation. Stimulator devices (Group 1) will be inspected to ensure appropriate function. Lead exit sites are inspected for skin irritation, infection, and inflammation. Maintenance, care of the leads and lead exit sites, and bandage changes will be performed as needed.

All subjects are asked to rate their worst, least, and average PLP and RLP (BPI #3, #4, and #5). Subjects will rate the degree with which pain has interfered with general activity, mood, walking ability, sleep, and enjoyment of life (BPI #9). Pain Disability Index (PDI) and Patient Global Impression of Change (PGIC) will be assessed. A medical reconciliation will be completed during each phone evaluation by asking the subject how many pills of narcotic pain medications they have left and querying the Virginia Prescription Monitoring Program Database.

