5.5.6 Visit 7, 8, and 9: Weekly follow-up telephone evaluations

Visits 7, 8, and 9 consist of weekly telephone evaluations at 5, 6, 7 weeks after starting peripheral nerve stimulation (Group 1) or discontinuation of peripheral nerve block (Group 2). If issues related to the

peripheral nerve stimulator device or leads occur that cannot be resolved by telephone, subjects may be evaluated in the Interventional Pain Clinic if needed.

Subjects are asked to rate their worst, least, and average PLP and RLP (BPI #3, #4, and #5). A medical reconciliation will be completed during each phone evaluation by asking the subject how many pills of narcotic pain medications they have left and querying the Virginia Prescription Monitoring Program Database.

5.5.7 Visit 10: Second outpatient clinic evaluation / up to 60 days after start of PNS

All subjects are asked to return to the Interventional Pain Clinic at approximately 60 days after starting peripheral nerve stimulation (Group 1) or discontinuation of peripheral nerve block (Group 2). Stimulator leads will be removed by gentle traction. The lead will be visually inspected by study staff to evaluate for lead fracture. In the case of a retained lead fragment, study staff will determine the most appropriate medical plan to further evaluate and treat the subject. In most instances, retained lead fragments do not need to be removed and are rarely associated with further complications. Lead exit sites are inspected for skin irritation, infection, and inflammation. Both groups will continue to be treated with SMT as needed until the end of participation in the study. Subjects in Group 1 are encouraged to complete the entire 60-days of peripheral nerve stimulation, however are free to discontinue treatment at any time during the treatment phase.

5.5.8 Visits 11, 12, and 13: Phone evaluations at 3, 6, and 12 months after study enrollment

Telephone evaluations for both groups occur at approximately 3, 6, and 12 months after study enrollment. Outcome measures to be assessed are listed in the Schedule of Study Procedures.

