7.2 Potential Risks

The devices used in this study have been cleared by the United States Food and Drug Administration to provide postoperative analgesia. Potential risks include infection, lead fracture, lead migration and/or dislodgement, nerve injury, bleeding, skin irritation, increased pain, and discomfort on insertion, during use or with withdrawal. However, there may be other risks that are currently unknown. The incidences provided are all estimated except for lead fracture. The risks listed below are described as either common (occurring more than 10% of the time), uncommon (occurring about 2-10% of the time), or rare (occurring less than 1% of the time).

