7.2.1 Infection

Based on previous studies using this PNS system, the risk of infection is rare. When compared to continuous femoral nerve block and/or continuous sciatic nerve blocks, the risk of infection from a percutaneously placed lead near these nerves is expected to be lower. The risk is thought to be mitigated by the inherent structure and design of the lead. Unlike nerve block catheters, PNS leads do not have an internal conduit through which bacteria can enter the body. The coiled structure of the fine wire lead allows it to stretch when pulled, rather than move into or out of the insertion site. This is thought to minimize the potential of introducing bacteria into the body. Lastly, the electrode is designed to have a tight electrodeskin barrier to help prevent bacterial inoculation. Infection risk will be minimized by using sterile leads and thoroughly cleansing the insertion site with antibacterial solution at the time of insertion. The insertion site will be covered with a dressing to keep it clean and dry, and the subjects will be instructed to inspect the site for signs of infection or irritation regularly and to inform the investigator if they occur. If infection occurs, the investigator may administer an antibiotic and/or remove the lead.

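### The four safety prompts in Section 8.1 omit infection, nerve symptoms and lead migration, so telephone ascertainment of these listed risks depends on volunteered reports unless Form AE already asks

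*Combined protocol and SAP*

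**What the plan says.** Section 7.2 opens its list of device hazards with "Potential risks include infection, lead fracture, lead migration and/or dislodgement, nerve injury, bleeding, skin irritation, increased pain" and goes on to discomfort. Sections 7.2.1 to 7.2.7 take these one by one. Infection and nerve injury are classed as rare (below 1%). Migration or dislodgement and lead fracture are classed as common (above 10%).

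Section 8.1 calls for monitoring at each follow-up encounter and then says what is asked: "Subjects will be asked if they are experiencing any increased discomfort, pain, skin irritation, or bleeding". The same section provides for examination of the exit site at outpatient visits and tells subjects to report any change in their medical condition.

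On the visits, Section 5.5 states "The study includes 13 Visits". Section 5.5.4 says "Visits 3, 4 and 5 consist of weekly telephone evaluations at 1, 2 and 3 weeks after starting peripheral nerve" stimulation. Section 5.5.6 repeats this for weeks 5, 6 and 7, and Section 5.5.8 has "Telephone evaluations for both groups occur at approximately 3, 6, and 12 months after study enrollment". For the weekly calls, Sections 5.5.4 and 5.5.6 list pain ratings, a pill count and a prescription-database query. They add that device or lead problems which cannot be settled by telephone may be seen in clinic.

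Staff inspect the exit site for infection during the daily hospital evaluations (5.5.3) and at the clinic visits (5.5.5, 5.5.7). Section 5.5.3 expects that "subjects in Group 1 will likely be discharged 7 to 14 days after starting peripheral nerve stimulation". Between inspections, Section 7.2.1 relies on the patient: "subjects will be instructed to inspect the site for signs of infection or irritation regularly".

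**The concern.** The risk list and the prompt list do not match. Where an event has a prompt, every subject is asked about it on a known schedule. Where it has none, it is recorded only if the subject raises it or staff happen to see it, and how often that happens varies between subjects and sites of lead placement.

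This matters because evaluating safety is a stated purpose of the pilot (Section 6.0, sample size), and Section 8.1 says adverse events are documented so that the system's safety profile is better understood. Systemic infection is the first example Section 8.0 gives of a reason to stop stimulation. An unreported dislodgement has a second cost: it conceals that the subject was no longer receiving the treatment whose feasibility is being assessed.

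**Working it through.** **1. Risks against prompts** (Sections 7.2.1 to 7.2.7 against 8.1)

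| Risk | Class in 7.2 | Named in 8.1? | Other coverage |
|---|---|---|---|
| Infection | rare | no | staff inspection in hospital and at Visits 6 and 10; self-inspection; partial overlap with skin irritation and pain |
| Lead fracture | common | no | lead examined by staff at removal |
| Migration or dislodgement | common | no | partial overlap with discomfort |
| Nerve injury | rare | no | symptoms expected within 24 to 48 hours (7.3), normally in hospital |
| Bleeding | rare | yes | |
| Skin irritation | common | yes | |
| Discomfort or increased pain | worsening pain common | yes | |

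Four headings have no named prompt. Fracture is found by staff looking at the lead, so a question to the subject adds little there until after removal. That leaves three: infection, nerve injury, and migration or dislodgement.

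**2. Visit count** (Sections 5.5.1 to 5.5.8)

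The plan's own total is reproduced: Visit 1 + Visit 2 + Visits 3–5 + Visit 6 + Visits 7–9 + Visit 10 + Visits 11–13 = 1 + 1 + 3 + 1 + 3 + 1 + 3 = 13.

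- All follow-up, Visits 3–13: 11 visits, of which 9 are by telephone (3, 4, 5, 7, 8, 9, 11, 12, 13); 9/11 = 82%.
- With a lead in place, Visits 3–10: 8 visits, of which 6 are by telephone; 6/8 = 75%.

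The second count is the relevant one for an indwelling lead, because removal is planned at Visit 10. It is an upper limit. If stimulation ends near day 30, only Visits 3–6 count, and 3 of those 4 are by telephone. If discharge is on day 14, Visits 3 and 4 (weeks 1 and 2) fall during the hospital stay, leaving 4 calls (5, 7, 8, 9).

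**3. Gaps between scheduled staff inspections**

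Inputs, in days from the start of stimulation: discharge 7 to 14 (5.5.3); Visit 6 at 28 to 30 (text and heading of 5.5.5); Visit 10 at 56 to 60 (8 weeks in the Schedule, about 60 days in 5.5.7).

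- Discharge to Visit 6: shortest 28 − 14 = 14 days; longest 30 − 7 = 23 days.
- Visit 6 to Visit 10: shortest 56 − 30 = 26 days; longest 60 − 28 = 32 days.

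**4. What eight treated subjects can show**

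The chance that at least one event occurs among 8 subjects is 1 − (1 − p)^8.

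- p = 1% (upper edge of rare): 1 − 0.99^8 = 7.7%.
- p = 10% (lower edge of common): 1 − 0.90^8 = 57%.

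These are chances that an event happens, not that it is missed. At least one migration or dislodgement is therefore more likely than not, and in a group of 8 one unrecorded event shifts the reported rate by 1/8 = 12.5 percentage points.

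**The case against.** The strongest reply is that one sentence is being made to carry the whole safety plan. Section 8.1 does not call its list exhaustive. It requires monitoring at each follow-up encounter and invites reports of any change. The Schedule, whose table is broken in extraction, appears to mark adverse-event assessment at Visits 3 to 13. Section 7.2.3 describes migration as something that may be felt as discomfort, which is prompted. Section 7.3 expects symptoms of nerve injury within 24 to 48 hours, when subjects are normally inpatients seen daily. Unscheduled visits are available (5.5.9).

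Much of this stands, and it rules out several stronger readings that a reader might draw:

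- *That the exit site goes unseen for weeks.* Only scheduled inspection by study staff is absent; subjects are told to inspect it themselves.
- *That fever, drainage, numbness or weakness are never asked about.* They are not named in the stated prompts. Form AE and the other case report forms are not in the documents and may contain them.
- *That classing infection and nerve injury as rare would rest on this trial's unprompted reports.* Section 7.2.1 bases it on earlier studies of the system for infection, and Section 7.2 calls every incidence except lead fracture an estimate. Eight treated subjects could not confirm it with any checklist.
- *That 9 of 11 is the count of calls with a lead in place.* Three of the nine come after planned removal.

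What the reply does not answer is systematic ascertainment. A mark in the Schedule says that adverse events are assessed, not what is asked; Section 8.1 supplies that content and leaves these items out. Discomfort is only a possible sign of migration, and a lead that has come out need not hurt. Coverage of the leg by paresthesia is re-assessed in hospital (5.5.3) but is not listed for the calls. The 24 to 48 hour window runs from needle placement, and Section 5.5.2 allows a dislodged or broken lead to be replaced, possibly after discharge. Some sciatic leads are placed by a gluteal approach (5.5.2), plausibly a hard site for a recent amputee to inspect.

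**Conclusion.** The point holds in a limited form. The prompts stated in Section 8.1 are incomplete against Section 7.2. Between discharge and Visit 6 (14 to 23 days), and between Visits 6 and 10 (26 to 32 days), telephone detection of infection, new sensory or motor symptoms and lead movement depends on what subjects volunteer. Up to 6 of 8 scheduled visits with a lead in place are affected. Existing safeguards reduce the gap without closing it.

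After Visit 10 the exposure is smaller but not nil. Section 7.2.2 treats fracture as common and recognises infection or granuloma from a retained fragment, while Visits 11 to 13 are all calls.

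The conclusion assumes that Form AE holds no fuller prompt list, and that the discharge interval in Section 5.5.3, which rests on length-of-stay data for transfemoral amputation, also serves for transtibial. Earlier discharge would lengthen the first gap. No efficacy outcome or analysis is affected. This is an inexpensive improvement to ascertainment, not a flaw that threatens the trial.

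**What to change.** Check Form AE first. If it already prompts for these events, cite it in Section 8.1 and the point is closed. If not:

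- Replace the four-item list in Section 8.1 with a fixed yes/no checklist aligned to Section 7.2. Keep the present items and add signs of infection at the lead or removal site (fever, redness, drainage, swelling), new numbness or weakness, and lead movement, dislodgement or loss of paresthesia.
- Use it at every telephone and clinic visit. At Visits 11 to 13, replace the items on an indwelling lead with items on the removal site and any retained fragment.
- Ask the non-device items in identical words in both groups, and enter every yes on Form AE.
- Keep the open-ended instruction to report any change.

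The cost is one protocol sentence, one case report form page and a minute or two on calls already scheduled. Prompting will bring in more minor adverse events, in both groups for the non-device items, so the report should state that events were elicited by checklist. No treatment rule or visit schedule changes.

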7.2.2 Lead fracture

Lead fracturing beneath the skin is a common risk, with most or all fractures occurring during the procedure to remove the lead. When this occurs, one or more lead fragments may remain in the body. Granuloma (mild tissue inflammation) is directly related to the risk of retained electrode fragments. The investigators will inspect the lead after removal to determine if any fragments were retained in the body. If there is suspicion of a retained fragment, the investigator will determine if removal of the lead is medically necessary. In most cases, removal is not necessary unless there are further sequalae associated with the fragment, such as infection or granuloma. Retained fragments may also be removed if the subject desires. The impact of retained fragments *in situ* is minimal and in most cases, retained fragments do not need to be removed.

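### The three adverse event severity classes in Section 8.1 are not exhaustive and mix intensity, treatment and seriousness, so some foreseen untreated events fit no grade

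*Combined protocol and SAP*

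**What the plan says.** Section 8.1 of the combined protocol and SAP gives three severity classes. The lower two are "mild (event that causes mild discomfort or inconvenience and resolves without treatment), moderate (event that requires medical intervention or medication to treat"). The top class is "severe (event that requires intervention to prevent permanent impairment or damage, an event that requires or prolongs hospitalization". That class also takes in events with lasting disability or harm, danger to life or a fatal outcome. The same section requires serious adverse events to reach the IRB within 5 days. It sends any observed adverse event to Form AE with its relation to the device and any treatment given, and it states that "AEs will be followed to resolution".

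The risk sections describe events that have to be graded on this scale:

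- **Lead fracture.** Section 7.2.2 says "Lead fracturing beneath the skin is a common risk", and Section 7.2 defines that term as "common (occurring more than 10% of the time"). Section 7.2.2 adds that fragments may be left behind and that "in most cases, retained fragments do not need to be removed".
- **Worsening pain.** Section 7.2.7 also calls this common. It gives no intensity and says "worsening pain is expected to be transient, resolving without additional treatment". The same section lets a subject who has pain from stimulation lower the output or switch the device off.
- **Intolerable pain.** Section 8.0 gives this as one example of a reason for the investigators to end PNS.

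**The concern.** A severity scale should give every adverse event exactly one grade, and the grade should describe how bad the event was. The scale in 8.1 uses a different yardstick at each level. Mild combines low intensity with spontaneous resolution. Moderate depends only on whether treatment was needed. Severe consists mainly of the criteria normally used to define seriousness. An untreated event that is either more than mild or persistent can therefore fall between the classes, and the investigator has to choose a grade without a rule.

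Safety is part of this pilot's stated goal (Section 1.2) and part of the justification for 16 subjects (Section 6.0, Sample Size). Section 8.1 says that events are reported to improve understanding of the device's safety profile. Section 6.3 specifies no analysis of adverse events or lead fractures, and the Schedule of Study Procedures has no fracture or fragment item. The descriptive record on Form AE therefore carries most of the safety information passed to the larger trial.

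The merging of severity with seriousness has a separate practical effect. The 5-day IRB rule depends on an event being serious, but 8.1 neither defines serious nor says that it means severe.

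**Working it through.** The plan states no figure on this point, so there is nothing to reproduce. The check is a literal classification, followed by a calculation of scale.

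**Step 1. Classify foreseen events by the 8.1 definitions.** Mild needs both mild discomfort or inconvenience and resolution without treatment. Moderate needs intervention or medication. Severe needs one of its listed criteria.

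| Event | Mild? | Moderate? | Severe? | Result |
|---|---|---|---|---|
| Mild worsening of pain, settles untreated | yes | no | no | mild |
| Fragment with infection or granuloma, treated | no | yes | no | moderate |
| Symptom-free fragment left in place | no, does not resolve | no, untreated | no | no class |
| Marked pain that ends when the subject switches the device off, not disabling | no, more than mild | no medical act | no | no class |

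The fragment in the third row also has no end point under the rule that events are followed to resolution.

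**Step 2. Scale: chance of at least one lead fracture in the PNS group.** Inputs:

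- 8 subjects in the PNS group (Section 6.0, Sample Size).
- One or two leads each (Sections 5.1 and 5.5.2), so 8 to 16 leads before any replacement.
- A fracture probability of 10% per lead, the floor of common in Section 7.2.
- Independence between leads, which is an assumption.

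Formula: P(at least one) = 1 − (1 − p)^n, with expected number np.

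- 8 leads: 1 − 0.9^8 = 1 − 0.430 = 0.57; expected 0.1 × 8 = 0.8.
- 16 leads: 1 − 0.9^16 = 1 − 0.185 = 0.81; expected 0.1 × 16 = 1.6.

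Common has no upper bound in the protocol. At an assumed 20% the chances are 83% and 97%; at an assumed 30% they are 94% and 99.7%.

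**Step 3. From fracture to retained fragment.** The documents do not say what share r of fractures leaves a fragment. With p = 0.1r, the chance of at least one retained fragment is 1 − (1 − 0.1r)^n:

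- r = 0: 0%.
- r = 0.5 (assumed): 1 − 0.95^8 = 34% with 8 leads and 1 − 0.95^16 = 56% with 16 leads.
- r = 1: 57% and 81%, as in Step 2.

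No similar calculation is possible for marked pain, because the protocol gives no frequency by intensity.

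**The case against.** Several stronger readings are tempting, and the documents do not support them.

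- **That ungraded events would be dropped.** Entry on Form AE does not depend on grade. Leads are inspected for fracture at removal (Sections 5.5.7, 7.2.2 and 7.3), adverse events are assessed at follow-up Visits 3 to 13, and the forms are reviewed every 8 weeks (Section 8.0). The risk is to the grade, not to the record.
- **That retained fragments and marked pain are themselves rated common.** The label belongs to lead fracture and to worsening pain in general. Retention is described only as possible, and mild transient worsening fits the mild class.
- **That fracture is the most frequent device problem.** Migration or dislodgement, skin irritation and worsening pain are also called common, and the protocol does not rank them.
- **That 57% to 81% is the chance of an ungradable event.** It is the chance of a fracture.
- **That intolerable pain leading to discontinuation has no grade.** Under Section 8.0 the investigators end PNS, which can be read as a medical intervention and hence moderate. The gap is clearer where the subject acts alone, as Sections 5.5.7 and 7.2.7 allow.

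Four further objections have some force. Form AE is not in the documents and may already hold outcome or seriousness fields; even so, the definitions in 8.1 would need to match it. The protocol does not define an adverse event, so it is open whether a symptom-free fragment is one; that favours recording fragments independently of the AE form. No planned analysis or stopping rule uses the grade, which limits the damage to the descriptive safety summary. Finally, grading by intensity would still put a symptom-free fragment in the lowest grade, so a change of scale alone is not enough.

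**Conclusion.** The point holds as a defect in a stated rule. The three classes are not exhaustive, they mix intensity, treatment given and seriousness, and seriousness has no definition of its own although IRB notification depends on it. Untreated events that are more than mild, or that do not resolve, are left to the investigator's judgement. They may be graded inconsistently or too low, but they would still be recorded.

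The number of events affected cannot be stated. A lead fracture somewhere in the PNS group is more likely than not at the protocol's own minimum rate, if that rate applies per lead and leads are independent. The number of fragments left in place depends on a retention share that the documents do not give. The consequence is confined to the safety description. The pain comparisons and the other planned group comparisons in Section 6.3 do not use the grade. This is an inexpensive improvement worth making before the first lead is removed.

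**What to change.** In Section 8.1 and on Form AE:

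1. Grade severity by symptom intensity and effect on function, with classes that cover every event.
2. Record three further items as separate fields: seriousness, using the criteria now listed under severe; treatment given; and outcome, with an option for ongoing or permanent. State that the IRB rule follows the seriousness field.
3. Record lead fracture and retained fragment as yes or no for each lead at each removal, dislodgement or replacement. Report both per lead and per subject as a device outcome separate from AE severity. This step is needed because a symptom-free fragment would still receive the lowest intensity grade.

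The cost is a wording change and a form revision. The AE figures may look slightly less favourable. Inspection at lead removal and AE checks at follow-up are already planned, so no visit or procedure is added and clinical management does not change.
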